Horizons Community Solutions, based in Albany, GA, will be a primary partner in the proposed research. In addition, we will partner with four United Way 2-1-1 organizations (United Way of Greater Atlanta 2-1-1 (UWGA 2-1-1), United Way of Central Georgia 2-1-1, Chattahoochee Valley 2-1-1 in Columbus, and United Way of Southwest Georgia (SWGA)). This research is funded by the Centers for Disease Control and Prevention. A subcontract with Horizons Community Solutions and two fee-for-service agreements with UWGA 2-1-1 and United Way of SWGA have been established.

Setting and Location

Study procedures, including informed consent and data collection, will be done over the telephone from the offices of the Rollins School of Public Health, Emory University, or home offices (due to COVID-19, CITI certified staff have been approved to carry out research activities at home). Recruitment and preliminary screening will occur at UWGA 2-1-1 and United Way of SWGA. Day-to-day operations of the project and oversight of data collection will be conducted by a Sr. Associate Director of Research Programs with support from staff and graduate research assistants. The intervention will be delivered jointly by Emory and Horizons staff. Process evaluation interviews with 2-1-1 leaders and staff and intervention arm participants will be conducted by Horizons staff and Emory staff and students.

Population

The study population will consist of 2-1-1 clients/callers. To be eligible for participation in the **hybrid-effectiveness implementation trial (aim 1)**, participants must be: 18 to 70 years of age, able to speak English, and self-report BMI of 20 and above. Pregnant women will be excluded and only one member per household will be enrolled.

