Recruitment will occur either by phone, web, text messaging, or via flyer distribution. Flyers (or IRB approved flyer content) may be distributed by any of the four United Way 2-1-1 organizations (United Way of Greater Atlanta 2-1-1, United Way of Central Georgia 2-1-1, Chattahoochee Valley 2-1-1 in Columbus, United Way of SWGA). Flyers will contain the Atlanta 2-1-1 and United Way of SWGA contact information for those interested in the study. The flyer content is included for review prior to production of flyers. In addition, 2-1-1 organizations may use social media and work with local media, such as TV and radio stations, in promoting the study. Content shared with the media will be consistent with that included in the approved flier and interested individuals will contact their local 2-1-1 as outlined below.

Phone/Text method: Line agents, called Community Connections Specialists at the Atlanta 2-1-1 and United Way of SWGA will answer incoming calls and texts at random, which will reduce systematic selection bias. After fulfilling service requests for those being recruited via text, a line agent will text participants a canned statement and the link to the screener for them to complete on their own (canned statement is included for review). After fulfilling service requests for those being recruited over the phone, a line agent will screen and invite callers to obtain more information on the study. A quick screening question at the beginning of our 2-1-1 version of the recruitment script will facilitate efficiency in recruitment (i.e., only those who report interest in participating in a study on making homes more supportive of healthy eating of 5 or more (on a scale of 0-10) will continue to full eligibility screener). Eligible and interested callers will provide their contact information (name and telephone number) and be referred to Emory research staff for further screening and enrollment. Atlanta 2-1-1 line agents also answer calls for the Macon and Columbus 2-1-1s. We anticipate recruiting a large proportion of the sample from these two 2-1-1 regions (approx. 40%), 20% from United Way of SWGA, and 40% from metro-Atlanta 2-1-1.

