Flyer/Web method: Participating 2-1-1 agencies will have the option of creating a study information flyer for distribution (in-person or on their website). Content of this flyer includes information on study involvement, length, compensation, eligibility criteria, and study PI. Callers will have several different options (phone, text, or web link) to be connected to their local agency for preliminary screening.

We expect that 80% of callers will be eligible and based on our feasibility study, 50% will be reachable and interested in the research. We anticipate approximately 1700 callers will be referred to enroll **800** participants. Emory research staff will contact callers to describe the research activities in more detail, confirm eligibility, obtain verbal consent, and enroll them in the study. Participants will provide contact information for themselves and a person who can always locate them to aid in retention, and complete the baseline survey on the call. Following the completion of the baseline survey, we will call them two more times, to complete two dietary recalls. That will conclude their requirements for enrollment into the study. Both 2-1-1 and Emory versions of the eligibility screeners are included for review.

Recruitment for the assessment of implementation study (aim 2).

2-1-1 and Horizons leaders and staff and intervention arm participants will be selected for semi-structured interviews.

The following protocol will be used to recruit 2-1-1 and Horizons leaders and staff:

1. An introductory email notification and up to five reminders will be sent to selected 2-1-1 and Horizons leaders/staff inviting them to participate in interviews. Potential participants will be identified by the Directors overseeing the centers and/or have a study-related role. The email invitation will include a description of the study, study procedures, compensation for completing the semi-structured interview, etc. An opt-out option with instructions will be provided in the email notification and no further contact will be made with those who remove themselves from further participation.

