Participants will be randomized within site (i.e., Atlanta, Albany, Macon, Columbus) using a random number generator with balanced blocks of 10. To accommodate rolling enrollment, the lead statistician or Associate Director of Research Projects will receive participant IDs in meaningful time intervals (e.g., weekly) and communicate their group assignment to the intervention Coordinator.

Intervention Condition

The intervention is designed to target home-based environmental determinants of dietary behaviors (Figure 4). The intervention is grounded in empirical research showing associations between environmental factors and behaviors. The

intervention is also informed by Social Cognitive Theory and the Social Ecological Framework,^{17,59} both of which posit reciprocal influences between individuals and their environment.

Intervention strategies are also informed by coaching, goal-setting theory, and motivational interviewing.⁶⁰⁻⁶³ Our coaching approach is adapted from

Figure 4. Conceptual Model of Healthy Homes/Healthy Families Intervention

[figure not shown]

Table 3. Intervention Delivery Schedule

Timing by Week	Type of Contact	Description
0	Recruitment, consent, baseline data collection	Home environment profile generated and mailed, with other intervention materials (family contract, healthy actions, stickers)
1	Call	Coach call to review profile and select healthy action 1
2	Text/email message	Reinforce actions with tips
3	Call	Reinforce progress/problem-solve challenges
4	Text/email message	Reinforce actions with tips
5	Call	Coach call to select healthy action 2
6	Text/email message	Reinforce actions with tips
7	Call	Reinforce progress/problem-solve challenges
8	Text/email message	Reinforce actions with tips
9	Call	Coach call to select healthy action 3
10	Text/email message	Reinforce actions with tips
11	Call	Reinforce progress /problem-solve challenges
12	Text/email message	Reinforce actions with tips

Heimendinger's 5-stage model (discover, connect, create, design, activate).⁶⁰ Additionally, the coaches will use Version #7

Version Date: 1/24/24

[figure not shown]

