To assess the effectiveness of the HH/HF in the 2-1-1 population we will conduct traditional RCT analyses, using both complete case and intent-to-treat data (all participants). We will first assess statistical significance of change between baseline and each follow-up points with appropriate bivariate tests (e.g., independent t-tests, Wilcoxon-Mann-Whitney tests, chi-square tests of independence). We will use growth modeling as the intent-to-treat analysis as it allows for modeling of all available data without the need for multiple imputations based on the assumption of data missing at random.^{71,72} Hence, we will include any variables identified as being related to missingness into these models as covariate. We will utilize multiple imputation if there are issues with missing data for individual covariates.⁷³ In general, growth models will include time (calculated as time elapsed between the measurement point and baseline date) and an interaction effect between time and group assignment. We will assess the intraclass correlation (ICC) due to clustering in 2-1-1 call centers, but based on our previous research, ICCs are expected to be very small (< 1%) and we therefore do not anticipate the need to adjust for clustering. However, if the need arises, we will adjust for clustering using three-level modeling with Bayesian estimators due to the small number of clusters.

Furthermore, we will test differences in intervention effectiveness, i.e., conduct moderator analyses, for demographics/household characteristics, and baseline BMI using growth modeling with interaction effects between group assignment and the moderators of interest. Finally, we will use Structural Equation Modeling to assess changes to the home food environment as mediators as indicated in Figure 4. Data cleaning and analyses will be conducted using SAS 9.4 and Mplus 8.

We will also use the addresses of HH/HF study participants to investigate the relationship between food desert residence and primary and secondary outcome variables such as diet quality and household food inventories. To do so, participants' addresses will be geocoded using ArcGIS 10.8.2 and assigned to 2010 census tract data. These data will then be joined with USDA's Food Access Research Atlas dataset, which includes census tract-level information on food access. Using participant's census tract as an objective indicator of food access de-identifies participants' home locations.

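### The 4- and 9-month tests of change do not adjust for the baseline value, and site, the randomisation stratum, has no default term in any outcome model

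*Combined protocol and SAP*

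**What the plan says.** Under DATA ANALYSIS, in the plan for the hybrid-effectiveness implementation trial, the first step is: "We will first assess statistical significance of change between baseline and each follow-up points with appropriate bivariate tests". The examples given are the independent-samples t, Wilcoxon-Mann-Whitney and chi-square tests. These compare the two groups and take no covariate. No ANCOVA or other baseline-adjusted comparison at a visit is described. The same paragraph promises both complete-case and intent-to-treat analyses and names growth modelling as the latter. Its terms, the interaction being with group, are given as follows: "In general, growth models will include time (calculated as time elapsed between the measurement point and baseline date) and an interaction effect between time". Variables found to be related to missingness are added as covariates.

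On site, the Randomization section says: "Participants will be randomized within site (i.e., Atlanta, Albany, Macon, Columbus) using a random number generator with balanced blocks of 10". The analysis plan lists no site term in the growth, moderator or mediation models. It says instead: "We will assess the intraclass correlation (ICC) due to clustering in 2-1-1 call centers". It expects an ICC below 1% and therefore no adjustment, but adds: "if the need arises, we will adjust for clustering using three-level modeling with Bayesian estimators due to the small number of clusters". It gives no ICC value that would count as a need. The by-site analyses described for aim 2 concern data from 2-1-1 and Horizons leaders and staff, not the trial outcomes.

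**The concern.** The protocol gives its two follow-ups different purposes (Field Methods for the trial): four months for short-term outcomes, nine months for maintenance. As listed, the growth model has one elapsed-time term and its interaction with group, so it yields a difference in slope rather than a separate effect at each visit. The bivariate tests are the only described analysis that addresses each visit directly, and the only one that fits the promised complete-case analysis. They are therefore likely to be reported. A change score subtracts the whole baseline value whatever its correlation with follow-up, and so carries more noise than an analysis that estimates the baseline coefficient. The baseline outcomes are collected anyway.

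For site, the usual expectation is that a stratification factor appears in the model. Here its inclusion rests on looking at the data: an ICC check without a threshold, or a screen for predictors of missingness. What is at stake is prespecification and agreement with the design, not error control.

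**Working it through.** **Inputs.** About 800 participants enrolled (Recruitment, Aim 1), read as 400 per arm; follow-up at 4 and 9 months; expected ICC below 1%. The available text gives no baseline-to-follow-up correlation (rho), standard deviation, significance level or power, so there is no plan figure to reproduce. Assumed: rho 0.3, 0.5 and 0.7; two-sided 5% level.

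**1. Visit-wise comparison, equal variances.** For n per arm, in units of sigma²/n:
- change score: 4(1 − rho)
- ANCOVA: 2(1 − rho²)
- ratio: (1 + rho)/2

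| rho | Change | ANCOVA | Variance reduction | CI narrower by | ANCOVA power if change test has 80% |
|---|---|---|---|---|---|
| 0.3 | 2.80 | 1.82 | 35% | 19% | 93.5% |
| 0.5 | 2.00 | 1.50 | 25% | 13% | 89.9% |
| 0.7 | 1.20 | 1.02 | 15% | 8% | 86.0% |

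The interval gain is 1 − √((1 + rho)/2). For power at rho 0.3: (1.960 + 0.842)/√0.65 − 1.960 = 1.515, which gives 93.5%.

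**2. Unequal variances.** With follow-up variance k times the baseline variance, the reduction is 1 − k(1 − rho²)/(1 + k − 2·rho·√k).
- k = 1.25: 28%, 17% and 7%
- k = 0.8: 42%, 34% and 25.5%

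**3. Simulation check.** Assumed: 614 analysed (76.8% of 800, the earlier trial's 12-month completion), sites 40/20/20/20% (even Macon/Columbus split assumed), site ICC 1%, 2,000 runs per setting. With normal data the change t-test had 78.7/79.2/79.2% power and ANCOVA with site 93.2/90.0/85.8%. Type I error was 4.4–5.5% and 4.4–5.2%. With skewed (lognormal) data, Wilcoxon on change had 76.4/75.8/73.6% power and rank-based ANCOVA with site 91.6/88.8/82.5%, both near 5% type I error.

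**4. Growth model as written.** Take a common baseline mean, linear time at 0, 4 and 9 months, compound symmetry and complete data. The 9-month group contrast then has variance
2·81·(1 − rho)/(97 − 169·rho/(1 + 2·rho)),
where 97 = 4² + 9² and 169 = (4 + 9)². At rho 0.3 this is 113.4/65.3125 = 1.736. At 0.5 and 0.7 it is 1.479 and 1.019. ANCOVA has 1.82, 1.50 and 1.02. If 40% supply baseline only (the pilot reached 60%), both are divided by 0.6: 2.894/2.466/1.698 against 3.033/2.500/1.700. So the growth model already has the precision that the change tests give up.

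**5. Site, ICC 1%.** Reduction in the ANCOVA standard error from adding site:
- site effect constant over time: 0.27/0.17/0.09%
- site effect at follow-up only: 1 − √((1 − rho² − 0.01)/(1 − rho²)) = 0.55/0.67/0.99%

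For the growth model with a constant site effect it is 0.36/0.20/0.09%. A separate 20,000-run simulation, without baseline adjustment, gave type I error 5.0% without site and 5.1% with it, and power 79.2% and 79.5%.

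**The case against.** The strongest reply is that the change tests are only a first step and the plan already recovers the lost precision in its intent-to-treat analysis. That stands. A reader might infer that the trial's main comparison forgoes 15–35% in variance; step 4 shows that it does not. The common-baseline reading needs assignment to follow baseline measurement. The recruitment section supports this, saying of the baseline survey and two recalls: "That will conclude their requirements for enrollment into the study". Nor are the change tests invalid or biased, since randomisation protects them.

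A reader might also infer that site can never enter a model, or that leaving it out inflates type I error. Neither is supported. Site could enter as a covariate related to missingness or through the three-level model, and step 5 shows no inflation.

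It is tempting to add that call centres differ from the strata, because "Recruitment and preliminary screening will occur at UWGA 2-1-1 and United Way of SWGA" and "Atlanta 2-1-1 line agents also answer calls for the Macon and Columbus 2-1-1s". But the flyer and web route sends callers to their local agency for screening, and the aim 2 analysis plan refers to four 2-1-1s. Call centres may simply mean the four sites, so a mismatch is not established.

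Finally, rho and the variance ratio are assumed, and the plan would transform non-normal outcomes, so the skewed-data simulation may not describe what would be done. The size is therefore uncertain. The direction is not: when ANCOVA estimates the baseline coefficient, its large-sample variance cannot exceed that of the change score.

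**Conclusion.** The point holds for the visit-wise and complete-case comparisons. These are valid but less precise than they could be, by 15% to 35% of the variance under equal variances and rho 0.3 to 0.7, and by 7% to 42% over the variance ratios examined. The intent-to-treat growth model, read as listed, is not affected. The practical gain is a sharper supportive estimate at each visit, chiefly at four months, which the growth model does not address separately.

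The site half is a matter of design and prespecification. At the top of the plan's expected ICC range the gain is under about 1% of the standard error. The reason to include site is that randomisation was stratified by it, and its inclusion should not depend on an unquantified check of the data.

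**What to change.** - **Continuous outcomes at 4 and 9 months:** replace the tests of change with ANCOVA of the follow-up value on group, baseline value and site, on a transformed or rank scale where needed. Label these analyses supportive of the growth model.
- **Site:** include it as a prespecified four-level fixed effect in the ANCOVA and the growth models, in place of the ICC-triggered switch to a three-level model.
- **Binary outcomes measured at baseline and follow-up:** use logistic regression on group, baseline value and site.
- **Binary outcomes defined by change, such as no weight gain:** adjust for the underlying baseline measure (here baseline weight) and site. For both kinds of binary outcome, note that the odds ratio is conditional on the covariates.

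The cost is SAP wording only. Baseline outcomes and site are already collected. The terms use one degree of freedom for the baseline value and three for site, four in all, out of about 800 participants.
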